**5. TREATMENT OF SUBJECTS**

This study does not contain any interventions.

**6. INVESTIGATIONAL PRODUCT**

Not applicable.

## 7. NON-INVESTIGATIONAL PRODUCT

### 7.1 Name and description of non-investigational product(s)

For the perfusion imaging part of each MRI exam, 0.1 mmol/kg of Dotarem or similar Gadolinium based contrast agent is administered intravenously.

### 7.2 Summary of findings from non-clinical studies

Not applicable

### 7.3 Summary of findings from clinical studies

Not applicable

### 7.4 Summary of known and potential risks and benefits

Not applicable

### 7.5 Description and justification of route of administration and dosage

Not applicable

### 7.6 Dosages, dosage modifications and method of administration

Not applicable.

### 7.7 Preparation and labelling of Non Investigational Medicinal Product

Not applicable.

### 7.8 Drug accountability

Not applicable

## 8. METHODS

### 8.1 Study parameters/endpoints

#### 8.1.1 Main study parameter

##### DCE-MRI

Kinetic modelling (10) will be applied in DCE-MRI images to assess quantitative kinetic parameters in the gross tumour volume related to blood volume, interstitial volume, flow and permeability. It will be tested whether different thresholds of haemodynamic parameters can predict disease free survival.

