### 4.4 Sample size calculation

It is expected to accrue at least 320 patients (section 4.1). With this sample size it is possible to identify a significant difference with a power of at least 80% in the entire cohort as well as in a subgroup analysis in high risk patients:

All patients:

Current retroEMBRACE 3/5y cancer specific survival: 81/74%

Hypothesis 3y disease free survival:

- Well perfused (50% of patients): 89%
- Poorly perfused (50% of patients): 73%

Sample size (log-rank test, 80% power 5% significance): 196 pts

N- and stage I+II:

Current retroEMBRACE 3/5y cancer specific survival: 90/87%

Hypothesis 3y disease free survival:

- Well perfused (50% of patients): 95%
- Poorly perfused (50% of patients): 85%

Sample size (log-rank test, 80% power 5% significance): 292 pts

N+ or stage III+IV:

Current retroEMBRACE 3/5y cancer specific survival: 69/57%

Hypothesis 3y disease free survival:

- Well perfused (50% of patients): 81%
- Poorly perfused (50% of patients): 57%

Sample size (log-rank test, 80% power 5% significance): 124 pts

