**Background for estimations of disease free survival and differences:**

In the entire patient cohort of Halle et al, 28% difference was found in progression-free survival with 40% and 75% progression free survival in poorly and well perfused tumours, respectively.

In the entire patient cohort of Mayr et al, 20% difference was found in disease free survival (3 years) with 60% and 80% disease free survival in poorly and well perfused tumours, respectively.

Assumptions for this study: We assume a 24% difference in cancer specific survival in the high risk group (N+ or stage III+IV), which is the mean of the difference found by Halle et al and Mayr et al. The reason that the difference is assumed in a high risk group and not in the entire group, is that disease free survival is significantly higher in retroEMBRACE than in the cohorts of Halle et al and Mayr et al. The survival reported by Halle and Mayr is more similar to the retroEMBRACE survival in the high risk group. For the low risk group (N- and stage I+II), 10% difference is assumed, and for the entire cohort 17% difference which is mean of 10% and 24%. The distribution between high and low risk patients is 50%-50%. We assume a selection of perfusion cut-point which divides the cohort into 50% well perfused and 50% poorly perfused, as was also the case in the study from Halle et al. With an overall sample size calculation based on the overall population, a number of 196 patients need to be enrolled. Sample size calculations in the high risk group indicate that with a sample size of 248 patients (2x124 patients), it is furthermore possible to observe a difference in the high risk group. It is not expected, that it is possible to perform a sub-group analysis in the low risk group with a sample size of 248 patients (a subgroup analysis in the low-risk group would require 2x292=584 patients).

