### **DCE-MRI**

The image analysis of the dynamic contrast enhanced scans will be done at Aarhus University Hospital by using a number of in-house scripts to determine the functional parameters; blood-flow, surface permeability, plasma volume fraction and barrier transport constant. From the complex image the arterial input function (AIF) will be extracted in the major feeding arteries using the work by Simonis et al. (34). Baseline T1 measurements derived from the prescans will be used to convert the signal measured in dynamic scan into contrast agent concentration. The measured AIF will be used in the convolution of the monoexponential impulse response function minimizing the difference to the measured tissue concentration curves, thus allowing the extraction of haemodynamic parameters (35,36).

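### The main analysis covers several DCE parameters at different thresholds, but the 5% level, 80% power and 196 patients hold only for one parameter at one 50:50 split, tested once

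*Protocol*

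**What the plan says.** The primary objective (section 2) is the sensitivity and specificity of DCE-MRI for picking out patients at raised risk of recurrence.

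Section 8.1.1, Main study parameter, derives "quantitative kinetic parameters in the gross tumour volume related to blood volume, interstitial volume, flow and permeability" and continues: "It will be tested whether different thresholds of haemodynamic parameters can predict disease free survival". The Summary repeats this. Section 9 (DCE-MRI) lists four extracted parameters: "blood-flow, surface permeability, plasma volume fraction and barrier transport constant". None is named as primary.

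Section 4.4 assumes 3-year disease-free survival (per cent) of "Well perfused (50% of patients): 89" and "Poorly perfused (50% of patients): 73", and gives "Sample size (log-rank test, 80% power 5% significance): 196 pts". Its background text adds: "We assume a selection of perfusion cut-point which divides the cohort into 50% well perfused and 50% poorly perfused". Planned accrual is larger than 196: "It is expected to accrue at least 320 patients".

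Leave-one-out validation is planned for the machine-learning outcome model (section 9) and is an option for computer-aided lesion detection (section 8.1.2). It is not stated for the DCE thresholds.

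**The concern.** The stated main analysis and the stated error rate and sample size describe different procedures. Section 4.4 is one dichotomy and one test. Section 8.1.1 is plural in both parameters and thresholds, on the same patients. If each comparison is judged at 5%, the chance that some DCE threshold appears predictive by luck exceeds 5%. If the threshold is also picked because it separates outcomes best, the sensitivity and specificity that the primary objective asks for are estimated on the data that chose it.

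At stake is whether a reported DCE threshold can be believed and would replicate in another cohort.

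**Working it through.** **1. Reproduce the plan's figure.** Inputs from section 4.4: 89% v 73% at 3 years, 50:50 split, 80% power, 5% level. Sidedness is not stated; two-sided fits.

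- Hazard ratio = ln(0.89)/ln(0.73) = 0.370
- Freedman events = (1.960 + 0.842)² × [(1 + 0.370)/(1 − 0.370)]² = 37.17
- Mean event rate = (0.11 + 0.27)/2 = 0.19
- N = 37.17/0.19 = 195.6, i.e. 196

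The same formula, rounded up to equal groups, gives the 292 and 124 stated for the two risk groups. Schoenfeld's formula (168) and one-sided variants do not fit. So 196 is the size for one two-sided 5% test of one split.

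**2. What that split implies for the primary objective.** Per 100 poorly and 100 well perfused patients there are 27 and 11 events. Sensitivity = 27/38 = 0.71, specificity = 89/162 = 0.55, and the Youden index is 0.26.

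**3. False-positive chance if tests are unadjusted.** The protocol does not give the number of thresholds, so a range is needed. Assumptions: no true effect, exponential survival with 81% at 3 years, censoring at 3 years, normally distributed parameters with correlation mostly 0 to 0.8, and log-rank tests at two-sided 5% in 196 or 320 patients.

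| Tests assumed | Chance of at least one p < 0.05 |
|---|---|
| One parameter, median | about 5% |
| One parameter, three within-tumour thresholds, each split at the median (correlation 0.9–0.95) | about 10–12% |
| One parameter, three quartile cut-points | 11–13% |
| Four parameters, median only | 17–18% (1 − 0.95⁴ = 18.5% if independent) |
| One parameter, nine deciles | 24–25% |
| Four parameters, three quartile cut-points | 31–41% (31% at correlation 0.8) |
| Four parameters, nine deciles | 55–69% |

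**4. Optimism if the threshold is chosen on outcome.** Assumed: best of four parameters over nine deciles, correlation 0.5; mean absolute difference in 3-year disease-free survival.

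| | N = 196 | N = 320 |
|---|---|---|
| No true effect, selected threshold | 15 points | 12 points |
| No true effect, fixed median split | 4 points | 4 points |
| True 16-point effect, selected threshold | 19.5 points | 17.4 points |

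At 320 patients with the assumed effect present, the excess is 17.4 − 16 = 1.4 points.

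**5. Power if the tests are corrected.** Freedman power = Φ(√(0.19 N) × 0.630/1.370 − z), with z the two-sided Bonferroni critical value.

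- Four tests (level 0.0125, z = 2.50): 62% at N = 196; 86% at N = 320. For 80% power: 53 events, 53/0.19 → 279 patients.
- Twelve tests (level 0.00417, z = 2.87): 48% at N = 196; 76% at N = 320. For 80% power: 66 events, 66/0.19 → 348 patients.

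**The case against.** **A SAP may settle this.** Only the protocol was available, and naming a parameter or a correction is often left to the SAP. The protocol nowhere says that each threshold is tested at an unadjusted 5%; that level appears only in the sample size lines. This stands, and it makes every error rate above conditional. It does not remove the mismatch, because section 8.1.1 affirmatively plans several thresholds of several parameters while section 4.4 is sized for one test. A correction added later would change the power stated for 196.

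**The thresholds may act inside the tumour.** The introduction stresses the tumour fraction with the weakest enhancement. A threshold could classify voxels and give one fraction per patient, which is then split 50:50 as section 4.4 assumes. This is a plausible reading and a milder one, but three such thresholds still give about 10–12%.

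**Nothing says that a cut-point is picked by outcome.** True. The median split in section 4.4 makes no reference to outcome. A reader might infer that the reported cut-point is bound to look better than it is; the protocol does not describe a procedure that would make this so.

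**The extreme figures need extreme assumptions.** A reader might cite a 73% false-positive chance, or an apparent Youden index of 0.13 from noise against the 0.26 implied by the plan. Both need four parameters scanned at 17 cut-points each (68 tests), which the protocol does not state. A single fixed median split, scored in either direction, already gives about 0.056 from noise.

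**The study is observational.** No treatment decision in the protocol depends on the result. This stands and lowers the severity.

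**Conclusion.** The point holds as an unresolved mismatch between sections 8.1.1 and 4.4. The 5% level, 80% power and 196 patients belong to one parameter at one 50:50 split tested once, and the main analysis as worded is wider than that.

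If the wider analysis is run unadjusted, modest assumptions put the false-positive chance between about 10% and 41%, and denser scans go higher. The number of tests and their correlation are assumptions, not protocol figures. Selection on outcome, if it happens, biases sensitivity and specificity upward: markedly without a true effect, slightly at 320 patients with the assumed one. The survival differences in the working show the size of this optimism; they are not themselves sensitivity or specificity.

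It would go too far to say that the error rate is certainly far above 5%, or that the study is too small. The planned 320 patients absorb a four-test correction, though not a twelve-test one at 80% power. Severity is moderate.

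**What to change.** In section 8.1.1, name one DCE parameter with one summary over the gross tumour volume, including any within-tumour threshold. Make its median split, already assumed in section 4.4, the single primary log-rank test at two-sided 5%. Label other parameters and thresholds exploratory.

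Alternatively, keep four parameters at the median as confirmatory with a Bonferroni correction, and restate the sample size: 279 patients for 80% power, or about 86% at 320.

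For any threshold searched on outcome, report a permutation or maximally selected log-rank p-value. Give cross-validated sensitivity and specificity, with the threshold chosen afresh within each fold.

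State how the high-risk comparison relates to the overall one. Whether it is tested only after the overall test succeeds, or shares the 5%, is the sponsor's choice.

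The cost is protocol or SAP wording, fixed before outcome data are analysed, and no patients beyond the planned 320. The downside is that other parameters and thresholds lose confirmatory status.

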#### 8.1.2 Secondary study parameters

Potential bias between centres will be evaluated for quantitative T2, quantitative DWI and DCE MRI parameters using ANOVA analysis. For DWI: the ADC (median tumour values) will be evaluated for assessment of any centre-effect.

We will investigate the use of machine learning techniques such as radiomics and deep learning in computer aided detection (CAD) of the primary lesion. The features used for this task will comprise of the full set and subsets of the functional and textural parameters extracted from DWI, DCE and qT2. The accuracy of the learned algorithm will be evaluated on a separate validation set with expert delineated primary lesion or a leave-one-out-cross validation.

Furthermore the DWI and qT2 will be tested whether they may predict disease free survival separately. The combination of all extracted functional (DCE, DWI, qT2) and textural features will be used to train a machine learning algorithm separating the classes: patients with and without disease free survival.

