al. (30) found prior to the onset of treatment that the highest 90th % ADC value correlated with response, similar finding was found by the group in Tianjin; Liu et al. (22). Both groups found that higher ADC value inside the tumour was predictive of poor response to treatment and suggest the higher ADC to be connected to tumour necrosis. When tumour necrosis occurs there is loss of cell membrane integrity and therefore an increase in the extracellular volume and a decrease in intracellular volume effectively increasing the ADC. Conversely, the group from London UK; Harry et al. (31) and Somoye et al. (32) showed no correlation to treatment response at the time prior to treatment. Instead the ADC at 2 weeks (and the change in ADC) into treatment was predictive of treatment response and prognostic of patient outcome. Finally, Marconi et al. (33) found a relation between minimum ADC in the tumour and both DSS and DFS.

Publication	Imaging marker	Endpoint	# patients
DCE-MRI			
Mayr (2012) (1)	FRV	LC, DSS	102
Mayr (2010) (2)	SI(10%)	LC, DSS, OS	98
Andersen (2012) (3)	nRSI(0.5min)	LRC	81
Loncaster (2002) (4)	median SI-I (Brix model)	DSS	50
Takayama (2009) (5)	$R_{down}$	TVRR	42
Semple (2009) (6)	$K^{trans}$	TVRR	20
Mayr (1998) (7)	RSI	LC	20
Mayr (1996) (8)	RSI	LC	17
Mayr (2000) (9)	RSI	LC	16
Mannelli (2010) (10)	$NE_F$	TVRR	13
Zahra (2009) (11)	$K^{trans}, k_{ep}$	TVRR	13
Gong (1999) (12)	$\Delta ME, \Delta PE$	TVRR	7
Andersen (2011) (13)	CVF ( $K^{trans}, v_e$ )	LC	81
Mayr (2009) (14)	SI(10%)	LC, DSS, OS	88
Huang (2014) (15)	SI	LC, DSS	102
Torheim (2014) (16)	texture features from GLCMs of $A_{Brix}$	PFS	81
Donaldson (2010) (17)	$E_F(25 \text{ sec})$	DFS	50
Mayr (2010) (18)	SI(10%)	No effect (for preRT alone)	62
Kim (2012) (19)	$K^{trans}, v_e$	No effect	35
Boss (2001) (20)	TTP, BAT	No effect	10
DWI-MRI			
McVeight (2008) (26)	$ADC_{pre(90\%)}$	TVRR	47
Liu (2009) (22)	Mean $ADC_{pre}$	TVRR	17
Somoye (2012) (32)	$ADC_{wk2}, \Delta ADC_{pre-wk2}$	OS, PFS	20
Harry (2008) (31)	$ADC_{wk2}, \Delta ADC_{pre-wk2}$	TVRR	20
Marconi (2016) (33)	$ADC_{min}$	DSS	66
Gladwish (2015) (30)	$ADC_{95}, nADC_{95}$	DFS	85

*Imaging marker abbreviation*

FRV: Function Risk Volume,  $R_{down}$ : the ratio of the number of down-sloped pixels to that of all selected pixels, SI:

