## 2. OBJECTIVES

*Primary:* To evaluate the sensitivity and specificity of dynamic contrast enhanced (DCE-MRI) to identify patients who have increased risk of disease recurrence (local, nodal, systemic) after radio-chemotherapy of cervix cancer.

*Secondary:* To apply radiomics for identification of patients who have increased risk of disease recurrence (local, nodal, systemic) after radio-chemotherapy of cervix cancer. Radiomics will include features from DCE-MRI, DWI and quantitative T2 imaging.

*Secondary:* To correlate functional imaging parameters with pathology, in a subgroup of patients

*Secondary:* To evaluate the implementation of quantitative imaging in a multicentre setting.

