### 8.2 Study procedures

#### 8.2.1 QA

Participating centres will have different scanning platforms, with different vendors and different generation of scanners providing more or less advanced sequences. Therefore the sequences for this study need to be optimized for each scanning platform to exploit its full potential. To ensure consistent quantification between the participating centres, a quality assurance procedure will be followed prior to inclusion of the first patient. This procedure consists of imaging of calibration phantoms with the proposed sequences for the study. The quantitative values will be compared to the ground truth phantom values. In addition, a set of benchmark sequences will be scanned. These consist of robust techniques that are available on each platform, but that typically are too slow for clinical use. Comparison of the obtained

values with the proposed study sequences and ground truth values will be done to assess the origin of potential differences in values so as to facilitate optimization of the study sequences. The results will be sent to the trial coordinators for analysis. Upon approval of the sequences specific for the centre by the trial coordinators, inclusion in the study in a participating centre can start.

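### Section 8.1.2 looks for bias between centres by ANOVA with no named adjustment for patient mix, so a centre difference in tumour values can reflect case mix, and a real offset can be masked.

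*Protocol*

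**What the plan says.** One of the secondary objectives in Section 2 is "To evaluate the implementation of quantitative imaging in a multicentre setting".

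Section 8.1.2 names the statistical test: "Potential bias between centres will be evaluated for quantitative T2, quantitative DWI and DCE MRI parameters using ANOVA analysis". It then adds: "For DWI: the ADC (median tumour values) will be evaluated for assessment of any centre-effect". No model terms, covariates or agreement limits are given, and the ANOVA is not linked to any phantom result. The quantity analysed is stated for DWI only. For quantitative T2 and DCE the sentence does not say which summary enters the ANOVA, although Section 8.1.1 takes the DCE parameters within the gross tumour volume.

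Section 8.2.1 explains why centres may differ: "Participating centres will have different scanning platforms, with different vendors and different generation of scanners providing more or less advanced sequences". It also sets up a separate check, in which "a quality assurance procedure will be followed prior to inclusion of the first patient". Calibration phantoms are scanned, and "The quantitative values will be compared to the ground truth phantom values". Slower benchmark sequences are scanned as well, and the coordinators must approve a centre's sequences before it starts to include patients.

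Section 9 (Tumour volume delineation) leaves the GTV contour to the treating institution.

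**The concern.** The question in Section 8.1.2 is about measurement, but for DWI the data are tumour values from different patients at each centre. A difference between centre means then has at least three sources: the scanner and sequence, the patients, and the local contour. ANOVA on centre alone cannot separate them.

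The protocol gives reason to expect that the patient part is not zero. Its review of the DWI literature (Section 1) reports of two research groups: "Both groups found that higher ADC value inside the tumour was predictive of poor response to treatment". The Summary hypothesises that low perfusion marks recurrence risk. Section 4.4 uses stage and nodal status to split the assumed 3-year disease-free survival (95/85% in the low-risk group, 81/57% in the high-risk group, well/poorly perfused). If these parameters carry prognostic information, they may well vary with stage and nodal status. Nothing in the design makes the mix equal across 8-15 centres.

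At stake is the answer to the multicentre objective. A difference in mix could be reported as centre bias, or a real offset could go unseen.

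**Working it through.** The protocol gives no figure for this analysis, so there is none to reproduce. The check asks how often an unadjusted ANOVA signals a centre effect when scanner bias is zero.

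**Inputs from the protocol**
- 8 centres, 10 patients per centre per year, 4 years (Section 4.1): 10 × 4 = 40 per centre, 320 in total.
- High-risk and low-risk patients split 50%-50% overall (Section 4.4).

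**Assumptions**
- High-risk share p spread evenly across the 8 centres over 50-50%, 40-60%, 30-70% or 20-80%.
- Mean difference d between risk groups of 0.3, 0.5 or 0.8 SD, with unit SD within a risk group.
- Two-sided patient differences only through risk group; test at the 5% level.

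**Formula.** With no scanner bias, the expected centre means differ by d × p. The one-way F-test (7 and 312 df, critical value 2.039) has approximate noncentrality

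λ = 320 × d² × Var(p) / (1 + d² × mean[p(1−p)]).

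**Worked case: shares 30-70%, d = 0.5**
- Var(p) = 0.4² × 9 / (12 × 7) = 0.01714
- mean[p(1−p)] = 0.25 − 0.01714 = 0.23286
- denominator = 1 + 0.25 × 0.23286 = 1.0582
- λ = 320 × 0.25 × 0.01714 / 1.0582 = 1.296
- rejection probability = 10.2%; the simulation gives 10.1%.

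For d = 0.8 the same steps give λ = 3.056 and 19.2%; the simulation gives 18.9%.

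**Simulated rejection rates with zero scanner bias (4000 runs per cell)**

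| High-risk share across centres | d = 0.3 | d = 0.5 | d = 0.8 | Adjusted for risk group |
|---|---|---|---|---|
| 50-50% | 4.9% | 5.0% | 5.2% | 4.9% |
| 40-60% | 5.4% | 6.1% | 7.9% | 4.9% |
| 30-70% | 6.8% | 10.1% | 18.9% | 4.9% |
| 20-80% | 9.2% | 18.7% | 41.9% | 5.1% |

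The adjusted test is the F-test for centre with risk group in the model.

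**Masking.** Take shares of 30-70% and d = 0.8, and set a real scanner offset of −0.8 × (p − 0.5). It runs from +0.16 SD at the centre with 30% to −0.16 SD at the centre with 70%, so it cancels the case mix exactly. This is a constructed worst case. The unadjusted test finds the offset in 5.1% of studies, the adjusted test in 21.4%. With equal mix the unadjusted test would find the same offset in 19.7%. An offset this small is usually missed even after adjustment, which is a reason to report estimates with intervals and not only a p-value.

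**The case against.** **The text does not say the ANOVA is unadjusted.** This is true. It names no covariates and excludes none, and a statistical analysis plan, not available here, may name them. An unadjusted test is the natural reading, not a stated one. What remains is that the protocol fixes the question as bias between centres, fixes tumour ADC as the DWI quantity, and names nothing that separates patients from scanners.

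**The phantom and benchmark QA already checks scanner bias.** A reader might infer that the ANOVA is the only evidence for the multicentre objective. Section 8.2.1 does not support that. The QA compares phantom values with ground truth and seeks the origin of differences, with no patient mix involved. It lessens the problem but does not remove it. It is described only before inclusion, with no repeat, and it cannot cover arterial input function extraction, motion or local delineation.

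**No consequence follows from the ANOVA.** A reader might also infer that a false signal would trigger correction of the perfusion parameter, or that a missed one would leave a biased common cut-point in use. No section links the ANOVA to a correction or to a threshold. Those consequences are conjecture and are not claimed here.

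**The size is assumed.** This stands. The protocol gives no case mix by centre and no SD difference between risk groups, and all centres recruit from EMBRACE II under the same eligibility rules. With modest differences in mix the error is small.

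**Conclusion.** The point holds in a limited form. A centre difference in patients' tumour values cannot by itself be read as measurement bias, and Section 8.1.2 names no adjustment that would help to separate the two. For DWI this follows from the text. For quantitative T2 and DCE it holds if tumour values are used there too, which Section 8.1.2 does not state.

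With 8 centres of 40 patients and a 0.3-0.8 SD difference between risk groups, false rejections run at about 7-19% for high-risk shares of 30-70%, and at 5-8% for shares of 40-60%. Adjusted for risk group they stay at about 5%. The mechanism is certain, but the size rests on the assumed mix and SD difference. The adjusted rates also assume that risk group is the only confounder.

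This concerns a secondary objective. It leaves the sample size and the primary analysis unchanged.

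**What to change.** In Section 8.1.2, state that:
- patient-level centre comparisons are adjusted for baseline stage and nodal status, by ANCOVA or a linear model with centre as a term;
- results are reported as centre offsets with 95% intervals;
- these offsets are read beside the phantom offsets from Section 8.2.1 before a difference is called measurement bias.

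Two further terms may seem natural but should stay out of the main model.
- **Vendor and field strength** are tied to centre, so adjusting for them would absorb the scanner bias being sought. In an illustration with 8 centres of 40, three vendors and assumed offsets of −0.5, 0 and +0.5 SD (true between-centre SD 0.42), the median estimated between-centre SD was 0.43 without a vendor term and about 0.00 with it (200 runs). Show vendor and field strength descriptively.
- **GTV volume** is drawn locally and partly carries a centre effect. Use it only in a sensitivity analysis.

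The cost is a sentence or two of wording and a few degrees of freedom. Clinical status at diagnosis is already reported on the EMBRACE CRFs (Section 8.2.4), so no new data should be needed. Differences in delineation between centres remain after this adjustment and should be named as a limit.
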